- 4) facilitate the neurointensive care of these patients including ventilatory support, the use of positive end-expiratory pressures, continued osmotherapy, and patient positioning; ultimately
- 5) better understand of pathophysiological processes with
- 6) immediately identify of complications with subsequent prompt intervention if needed.

QUESTIONS

- * Is infratentorial multimodal neuromonitoring safe and feasible, and necessary?
- * Do data assessed by multimodal monitoring in the posterior fossa correlate with data from the supratentorial compartment?
- * Is infratentorial multimodal neuromonitoring able to timely predict complications such as local swelling, mass effect, vasospasm, ischemia, or infarction?
- * Is infratentorial multimodal neuromonitoring of value in daily clinical practice?

HYPOTHESES

- The intracranial multimodal monitoring in the posterior fossa is safe and feasible, without any increased risk due to additional probes.
- Data generated by infratentorial multimodal neuromonitoring do not completely correlate with data from standardized supratentorial multimodal neuromonitoring. There are significant differences in ICP- or brain tissue oxygenation values between the supratentorial and infratentorial compartments.
- The infratentorial multimodal monitoring immediately detects all relevant complications related to posterior fossa lesions including mass effect, local swelling, postoperative hematoma, ischemic events, decrease in the blood flow, vasospasm and inadvertent or prolonged vessel occlusion, or infarction, resulting in prompt therapeutic intervention if necessary.
- Additional information from infratentorial probes facilitate to maintain the critical patients including ventilatory support, the use of positive end-expiratory pressures, continued osmotherapy, and patient positioning.

CLINICAL RELEVANCE

Our prospective study can provide better guidance and optimization of clinical therapy through a comprehensive assessment of patients harboring posterior fossa lesions.

This study has very high potential to generate a new intellectual property, to yield discoveries improving the prediction of complications and monitoring the effects of treatments. The data will offer better understanding of pathophysiological mechanisms in posterior fossa lesions.

STUDY DESIGN

METHODS

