In phase I of the study 15 patients with posterior fossa lesions who require prolonged neurointensive care and in which any intracranial invasive intervention is indicated regardless of used technique or treatment modality will be enrolled in the study. The indication for posterior fossa lesion treatment will be decided on a case-by-case basis by our neurosurgical team irrespective of the study.

The study will start as a monocentric clinical trial (pilot study), and subsequently in phase II the study is planned to be continued as a multicentric trial.

In the majority of patients, ICP- and LICOX sensors are usually placed in the right frontal lobe and/or at the site of the lesion. In case of posterior fossa surgery, additional probes (ICP / LICOX) will be placed into the surgical field.

The neuromonitoring data will be recorded and analyzed. Additionally, demographic data, all treatment-related complications, and management of intracranial hypertension will be recorded.

All adverse effects will be noted and reported, even if no clinical consequence will ensue. Non-neurological complications such as cardiopulmonary complications will be documented separately.

After the invasive treatment of the posterior fossa lesion, all patients will undergo CT and/or MRI as standard of care within 72 hours after the intervention (the acute phase) as a protocol for detection of procedure-related complications. As standard of care, an additional follow-up MRI will be performed if needed. In stable patients a preoperative MRI will also be performed before invasive treatment

The following outcomes will be evaluated and analyzed: mean ICP, ICP pulse amplitude, respiratory waves, slow waves and the RAP (compensatory reserve) index of supra- and infratentorial ICP signals, transtentorial difference, brain tissue oxygenation, blood saturation, ASTRUP, and further vital parameters, peri- and postoperative morbidity and mortality, procedure-related morbidity including infection, hematomas, epilepsy, cerebral puncture, cranial nerve palsies, and CSF leaks, perioperative cerebral ischemia, long-term neurological morbidity and mortality, and overall neurological outcome.

Institutional review board will be obtained by the Ethics Committee of the Medical University Innsbruck, Austria. Informed consent will be acquired from all patients for participation in the study during the study period according to local requirements.

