All treatment techniques and MRIs will be performed as a part of routine clinical care and no modifications will be introduced in the treatment or the follow-up modalities currently used by the Department of Neurosurgery and Neuroradiology, with the exception of ^{31}P - MRS (see above).

VARIABLES AND PARAMETERS

Clinical data

The following demographic characteristics of treated posterior fossa lesions and outcomes will be documented and analyzed: type, location, size, shape, volume, technical success of treatment, recurrence, bleeding / rebleeding, perioperative morbidity and mortality, procedure-related morbidity including thromboembolic events, iatrogenic rupture, perioperative stroke, occurrence of complications related to lesion (e.g. mass effect, delayed ischemia, hydrocephalus, vasospasm, etc.) long-term neurological morbidity and mortality, and overall good neurological outcome

Cerebral multimodal neuromonitoring

ICP, brain oxygen partial pressure (PtO₂) / **LICOX®**, alternatively microdialysis, cerebral blood flow / **Hemedex®**, cortical spreading depolarization (CSD)

MRI (including DWI and ³¹P-MRS in selected cases)

Phosphocreatin (PCr), Phosphomonoester (PME), Phosphoethanolamin (PEth), Phosphocholin (PCho), Phosphodiester (PDE), Glycero-Phosphocholin (GPC), Glycero-Phosphoethanolamin (GPE), Anorganisches Phosphat (Pi), Adenosin-Triphosphat (α , β , γ ATP), Adenosin Diphosphat (ADP), Mg²⁺, pH

INTERVENTION/EXAMINATION

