All patients suffering from symptomatic posterior fossa lesions are first treated and stabilized in the emergency room and/or at the ICU. After the initial imaging (in most cases CT/CTA), if necessary, patients are transported to the OR and/or the angiosuite. After treatment, regardless of the used treatment modality and possibly after implementation of invasive multimodal neuromonitoring according to contemporary guidelines by patient impaired consciousness (e. g., with GCS≤8), implantation of multimodal neuromonitoring is performed – please find the details in the study protocol TIBI-study (AN2014-0201 339/4.6 – microdialysis, tissue perfusion measurement, ICP-measurement, LICOX) the patients are transported to the neurosurgical or neurological ICU. In each patient, MRI including ³¹P-MRS will be performed at different stages of treatment (the indication for neuroimaging will be decided on a case-by-case basis). As mentioned above, in stable patients a preoperative MRI will also be performed which may provide additional relevant information for patient treatment.

Simultaneously, data from invasive multimodal neuromonitoring and laboratory values will be acquired and evaluated during the ICU stay after treatment.

All methods are validated by an international collaborative ring trial, as they are used in routine.

Finally, outcome scores like the mRS and the Glasgow Outcome Scale will be recorded.

INSTRUMENTS

➤ ***Multimodal Neuromonitoring***

- ICP-measurement, Raumedic, Münchberg, Germany
- Brain tissue oxygen and brain temperature, Licox, Integra, Plainsboro, New Jersey, USA
- Cerebral microdialysis, CMA, Stockholm, Sweden
- Alternatively tissue perfusion measurement, Hemedex, Cambridge, MA, USA

DISSEMINATION

A part of this study will most likely be assigned as a clinical Ph.D.-project for the residents at the Department of Neurosurgery.

STUDY POPULATION (SPECIMEN / TEST PERSON / PATIENTS)

IN- AND EXCLUSION CRITERIA

INCLUSION CRITERIA

- Posterior fossa lesions with anticipated prolonged neurointensive critical care
- Patients older than 18 years
- Informed consent if applicable (unconscious patients will be also enrolled)
- No existing exclusion criteria

EXCLUSION CRITERIA

- Coagulation disorders
- Age < 18 years
- Pregnancy

INFORMED CONSENT OF TEST PERSONS / PATIENTS

All patients harboring posterior fossa lesion who meet the inclusion criteria will be enrolled in the study.

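### Hypothesis 4 and question 4 (the infratentorial probes help care) have no outcome linked to them, and nothing records which signal prompted a change in care

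*Combined protocol and SAP*

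**What the plan says.** **The claims.** Under HYPOTHESES the fourth statement is "Additional information from infratentorial probes facilitate to maintain the critical patients", followed by ventilatory support, PEEP, osmotherapy and positioning. Aim 4 under AIMS OF THE STUDY covers the same ground. The fourth item under QUESTIONS is "Is infratentorial multimodal neuromonitoring of value in daily clinical practice"; value is not defined.

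**The outcomes.** METHODS (under STUDY DESIGN) says "The following outcomes will be evaluated and analyzed: mean ICP, ICP pulse amplitude, respiratory waves, slow waves and the RAP (compensatory reserve) index". The list goes on to the transtentorial difference, oxygenation, blood gases, vital parameters, morbidity, mortality and neurological outcome. VARIABLES AND PARAMETERS adds lesion, complication, monitoring and imaging data. INTERVENTION/EXAMINATION adds "Finally, outcome scores like the mRS and the Glasgow Outcome Scale will be recorded".

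**The nearest care item.** METHODS also states that "management of intracranial hypertension will be recorded". It appears apart from the outcome list, with no definition, trigger or analysis.

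**Who gets the probes.** METHODS says "In case of posterior fossa surgery, additional probes (ICP / LICOX) will be placed into the surgical field". The informed consent section says "All patients harboring posterior fossa lesion who meet the inclusion criteria will be enrolled in the study".

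**The comparison.** STATISTICAL ANALYSIS refers to two treatment groups and to study groups, without defining either.

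**Treatment.** VARIABLES AND PARAMETERS is preceded by the statement that "no modifications will be introduced in the treatment or the follow-up modalities currently used by the Department of Neurosurgery", with an exception only for phosphorus spectroscopy. The consent section repeats this.

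**The concern.** A hypothesis that the probes help care needs at least a record of care decisions and of what prompted them. A claim that care or outcome is better needs a comparison as well. The plan sets up neither. The comparison of supratentorial with infratentorial signals within a patient tells us whether the readings differ, which is hypothesis 2. It does not tell us whether anyone acted on the difference.

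What the second probe adds to the standard one is a stated motivation of the study. If the plan is followed exactly, that part of the report will rest on impression. The timing matters because a clinician's reason for a change has to be noted when the change is made. The traces do not contain it.

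**Working it through.** The plan gives no figure on this point. The sample size of 30 in CALCULATION OF THE NUMBER OF CASES is justified by incidence, with no effect size, rate, SD, power or margin, so there is nothing to reproduce. The check is mainly a trace from claim to data to analysis.

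**Step 1: trace hypothesis 4 and question 4.**

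| Claim | Listed outcome or variable | Trigger recorded | Planned analysis |
|---|---|---|---|
| Ventilatory support | none | no | none |
| PEEP | none | no | none |
| Osmotherapy | none by name; could fall under management of intracranial hypertension | no | none |
| Positioning | none by name; same remark | no | none |
| Value in daily practice | not defined | no | none |

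The count is 0 of 4 care items among the outcomes and variables. Blood gases and vital parameters are physiology, not decisions. The mRS and Glasgow Outcome Scale are not tied to either statement.

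**Step 2: look for a comparator.** Probes go to patients having posterior fossa surgery, and all eligible patients are enrolled. No randomised, concurrent or historical group without the probes is described. Patients treated in the angiosuite might have no infratentorial probe, but they are not designated as controls and would differ by treatment modality.

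**Step 3: what could be recovered afterwards.** If management entries carry times (the plan does not say), an analyst could count changes that followed an infratentorial rise without a supratentorial one. That is a temporal proxy. It cannot separate the signal from a clinical sign or a scan at about the same time, and it misses changes not entered as management of intracranial hypertension.

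**Step 4: what a trigger record would give.** For x of n patients, the Clopper-Pearson limits are:
- lower = the 0.025 quantile of Beta(x, n − x + 1)
- upper = the 0.975 quantile of Beta(x + 1, n − x)
- for x = 0, upper = 1 − 0.025^(1/n)

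The counts x are invented for illustration. The n of 15 is the phase I number in METHODS, and 30 is the number in the case-number section.

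| x/n | Estimate | 95% CI |
|---|---|---|
| 5/15 | 33.3% | 11.8% to 61.6% |
| 0/15 | 0% | 0% to 1 − 0.025^(1/15) = 21.8% |
| 10/30 | 33.3% | 17.3% to 52.8% |
| 0/30 | 0% | 0% to 11.6% |

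Fifteen is a ceiling for phase I. Enrolment is regardless of treatment modality, and the usual sensor sites are given as the right frontal lobe and/or the lesion, so not every patient need have both probes working. With 10 such patients (an assumption), 0/10 would give an upper limit of 1 − 0.025^(1/10) = 31%.

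**Step 5: would adding a comparator now be better?** Take 30 split 15 and 15, assumed rates of 50% and 30%, and two-sided 0.05 (sidedness assumed). With mean rate 0.4:
- power = Φ[(0.2·√15 − 1.96·√(2·0.4·0.6)) / √(0.5·0.5 + 0.3·0.7)] = Φ(−0.86) = about 20%
- 80% power needs [1.96·√0.48 + 0.842·√0.46]² / 0.2² = 93 per group

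A controlled test of benefit is out of reach at these numbers for a 20-point difference. A descriptive outcome is not.

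**The case against.** The strongest reply is that care facilitation is secondary. The stated goal is detection of dynamic changes and safety, AIMS OF THE STUDY says only that the monitoring may help to direct care, and phase I is a pilot. On that view, calling hypothesis 4 exploratory would be enough. This stands as to weight: the safety and paired-reading aims are unaffected. But the label alone still leaves nothing to report, and the log is inexpensive.

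A second reply is that the proposed outcome is itself a judgement, since an unblinded clinician names the trigger, and that a single-arm proportion shows use rather than help. Both parts stand. The outcome must be presented as descriptive.

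A third is that STATISTICAL ANALYSIS does name groups. It does, but they are undefined, so they supply no comparison of care with and without the probe.

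A reader might also infer that no estimate of any kind is possible, or that nothing can be reconstructed later. The documents do not support that: both signals are analysed and some management is recorded, so a temporal proxy may be available. Equally, a reader might infer that a trigger field would let the study confirm or refute hypothesis 4. It would not, because no comparator is added.

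**Conclusion.** The point holds in a limited form. Hypothesis 4 and question 4, one of four in each list, have no outcome linked to them, no recorded trigger and no defined comparison of care. Following the plan as written gives at most a temporal proxy for whether the infratentorial signal led to action. This is more than missing detail, because the reason for a change has to be captured at the time. It is a desirable improvement and not a threat to the study's other aims.

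With a trigger record, phase I could report a proportion with wide limits: 12% to 62% for 5/15, and an upper limit of 22% for 0/15. That is useful for planning phase II but is not evidence of patient benefit.

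The conclusion assumes that management entries carry no trigger, since none is mentioned, and that at most 15 patients in phase I have both probes working. The separate study protocol cited for monitoring details is not available here; it is cited for the implantation of monitoring, not for outcomes.

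The statement that treatment will not be modified may mean only that the study mandates no change. As worded, it sits awkwardly with a hypothesis that the probes inform care. The two must be reconciled; this review does not say which should prevail.

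**What to change.** **METHODS.** Record changes in the four care items named in hypothesis 4, together with management of intracranial hypertension. For each change, note the time and the trigger when the change is made: infratentorial signal alone, supratentorial signal alone, both, or clinical/imaging/other. A field added only to the existing hypertension entries could miss changes in ventilation, PEEP or positioning made for other reasons.

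**STATISTICAL ANALYSIS.** Report the proportion of patients with at least one change prompted by the infratentorial signal alone, with the Clopper-Pearson 95% CI that the plan already uses. The denominator is patients with both probes working; state that number.

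**HYPOTHESES and QUESTIONS.** Label the outcome descriptive and hypothesis 4 exploratory, and say that the proportion shows use of the signal, not benefit. Tie question 4 to the same outcome or define value otherwise.

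**Treatment statement.** Reconcile it, in both places where it appears, with hypothesis 4 and the log.

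**Cost.** A modest documentation load during the ICU stay. The main weakness is subjective, unblinded naming of the trigger, which affects the whole outcome and should be stated in the report. The recorded times allow a temporal check alongside. No additional patients or procedures are needed.

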In their initial experiments¹⁰ a balloon was placed in the extradural space in the posterior fossa in order to create a space-occupying mass, but with gradual inflation of the balloon stripping of the dura mater from the skull over the transverse sinus occurred, and the balloon expanded into the supratentorial space. Therefore, the infratentorial balloon was inserted in the subdural space over the lateral and inferior aspects of the cerebellum.

It is worthy of notice that a failure of communication of pressure from the infratentorial to the supratentorial space then occurred with inflation of the balloon. With small volumes of the balloon the intracerebral pressure was elevated to several times the subarachnoidal pressure over the corresponding cerebral hemisphere, and communication of pressure to the subarachnoidal space occurred gradually as the intracerebral mass was enlarged with additional injections. In contrast, transmission of pressure from the subarachnoidal space through the brain to the intracerebral balloon was invariably complete and virtually instantaneous.

In prior experiments¹⁴⁻¹⁶ performed by the Philadelphia group in which sustained increased intracranial pressure was produced by a gradually expanding extradural mass, the pressure within the extradural mass was equal to the pressure in the opposite extradural space in some animals, whereas in others it was many times the contralateral extradural pressure. This demonstrated that the dura mater can restrain significantly the expansion of an extradural mass and prevent transmission of pressure from the mass to the underlying brain.¹⁴ Likewise, it was found that a progressive failure of communication of pressure from the supratentorial to the infratentorial space occurs as cerebral tissue obstructs the tentorial incisura, and herniation of the cerebellar tonsils into the foramen magnum prevents transmission of pressure from the posterior fossa to the spinal canal.¹⁰ Thus, in these circumstances the brain does not transmit increased intracranial pressure.¹⁰

With the gradual expansion of an extradural mass, transmission of pressure from the mass to the brain is dependent upon the firmness of attachment of the dura mater to the inner table of the skull, its configuration in relation to the underlying brain, and its physical properties.¹⁷

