In the past, recording of ventricular fluid pressure has proved to be a reliable method in clinical neurosurgery, as shown by Lundberg et al.¹⁸⁻²⁰ Furthermore, some authors recorded supratentorial pressure during posterior fossa surgery with the intention of obtaining continuous information on the pressure state in major intracranial compartment.^{3, 21, 22}

Of note, some surgeons were reluctant to introduce direct subdural posterior fossa monitors for a number of reasons. Some of the possible problems may include cerebrospinal fluid (CSF) leaks, cranial nerve dysfunction, and the possibility of brainstem irritation with resulting autonomic dysfunction. Yet, many recent studies have showed the safety and feasibility of intracranial monitoring in the posterior fossa.^{1, 21, 23-26}

PRESENT

With regards to pathophysiology and clinical practice, the intracranial pressure (ICP) profiles in the supratentorial and infratentorial compartments remain unclear. After a neurosurgical operation in the posterior fossa there are most likely pressure differences between supra- and infratentorial spaces.²⁷ It is well known that the pressure within the skull is unevenly distributed, with demonstrated ICP gradients.²⁵ By contrast, Rieger et al²³ reported no significant differences between supratentorial and infratentorial ICP values in an animal model. The infratentorial ICP elevation in the presented pig model led to a uniform ICP elevation in the intracranial space without development of a considerable pressure gradient below and above the tentorium. Importantly, in the low pressure part of the ICP curve, cerebrospinal fluid connects the compartments and contributes to the pressure equilibrium.

To rely on autonomic changes or neurological deterioration as signs of a postoperative complication narrows the temporal margin of safety for the institution of treatment.

It has been the policy of our Department to electively monitor all complex posterior fossa procedures via a supratentorial intracranial multimodal monitoring; however, it remains unclear whether an acute change in the posterior fossa would be reflected by the supratentorial monitor prior to clinical deterioration.

Thus, we intend to apply the intracranial multimodal monitoring in both infratentorial and supratentorial compartments simultaneously. Such coincident measurements most likely will be the most sensitive way to assess focal swelling, ischemia and tissue perfusion in the posterior fossa structures.

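### ICP sensor plane and distance from the lesion are not stated to be recorded, so a systematic operative-site offset could be reported as a transtentorial difference

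*Combined protocol and SAP*

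**What the plan says.** Under Study Design – Methods, the infratentorial position is given in one sentence: "In case of posterior fossa surgery, additional probes (ICP / LICOX) will be placed into the surgical field". The sentence before it covers the usual sensors: "In the majority of patients, ICP- and LICOX sensors are usually placed in the right frontal lobe and/or at the site of the lesion". The comparator position is therefore also not fixed.

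The outcomes in the same section include the "index of supra- and infratentorial ICP signals, transtentorial difference, brain tissue oxygenation". The second hypothesis states: "There are significant differences in ICP- or brain tissue oxygenation values between the supratentorial and infratentorial compartments".

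The clinical data list (Variables and Parameters) covers the lesion's type, location, size, shape and volume, but not sensor position. CT and/or MRI within 72 hours is planned to look for procedure-related complications; locating probes is not mentioned. Intervention/Examination refers to the TIBI-study protocol for implantation details. That protocol is not among the documents, and the reference does not say whether it covers infratentorial probes. Statistical Analysis names Mann-Whitney U or Student t tests between groups at P<0.05, with no term for sensor position.

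**The concern.** An ICP reading may depend on the tissue plane of the sensor and its distance from a mass, as well as on its side of the tentorium. The plan puts one sensor at the operated site and the other usually in the frontal lobe. Compartment and nearness to the lesion therefore tend to vary together, and adding patients does not separate them. The surgical field could also mean a subdural, a parenchymal or a cavity position, so the plane may differ within a pair and between patients.

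Two conclusions are exposed. A difference could be declared between compartments where there is only a local difference at the operative site. An offset in the opposite direction could hide a real gradient. If position is not captured during the pilot, it may not be recoverable consistently before the planned multicentre phase.

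**Working it through.** **The documents' own evidence.** The history section reports on an experimental mass: "With small volumes of the balloon the intracerebral pressure was elevated to several times the subarachnoidal pressure over the corresponding cerebral hemisphere". No tentorium lies between those two sites. For extradural masses, pressure in the mass equalled the opposite side in some animals, "whereas in others it was many times the contralateral extradural pressure". The same section limits this evidence. The several-fold difference was seen at small balloon volumes, pressure was communicated gradually as the mass grew, and transmission from the subarachnoid space through the brain was complete and almost immediate. The first sentence may also describe pressure at the balloon itself rather than in nearby tissue. The evidence shows that a site effect within one compartment is possible. It gives no size for a postoperative patient.

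**Plan figures.** There is nothing to reproduce. The plan gives 15 patients for phase I (Methods) and 30 in the case-number section, with no effect size, SD or power.

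**Illustration; every ICP input is assumed.** The true compartment difference is 0. Paired differences have SD s = 3–5 mmHg. Half the patients carry a local offset b = 2–5 mmHg. The test is a two-sided paired t test at 0.05.

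*Offset always in the same direction.* The apparent mean difference is 0.5b and the variance is s² + b²/4. The standardised shift is 0.5b/√(s² + b²/4) × √n.
- b = 2, s = 5: 1/5.10 = 0.196; times √15 = 0.76, times √30 = 1.07.
- b = 5, s = 3: 2.5/3.91 = 0.640; times √15 = 2.48, times √30 = 3.51.

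Simulation with 100,000 runs per setting gives these rates of false significance:

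| Assumption | n = 15 | n = 30 |
|---|---|---|
| Same direction, paired t | 11–63% | 18–92% |
| Random sign, paired t | about 5% | about 5% |
| Same direction, unpaired t, shared between-patient SD 5 mmHg | about 0.2% to 8–9% | about 0.3% to 29–30% |

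*Offset of random sign.* The mean is 0 and the variance is s² + b²/2, so the error rate is unaffected but precision falls. With s = 4 and b = 5, the SD rises from 4 to √(16 + 12.5) = 5.34 mmHg. The difference detectable with 80% power is 0.778 SD at n = 15 and 0.529 SD at n = 30. It rises from 3.1 to 4.2 mmHg and from 2.1 to 2.8 mmHg respectively.

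*Unpaired test.* This row is the closest to the tests that the plan names. Treating paired readings as independent groups makes the test conservative when patients differ widely, so several settings fall below 5%.

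**The case against.** The strongest reply is that operative-site pressure is what the study wants: the stated goal is to detect dynamic changes in the operative compartment. That stands. Measuring local pressure is not the fault; reporting it as a transtentorial difference without knowing sensor position is.

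Second, the background is mixed. Besides the complete transmission noted above, the section headed Present cites an animal model with no considerable gradient across the tentorium. This also stands: a placement artefact is possible, not shown.

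Third, implantation may be standardised elsewhere. The TIBI protocol might fix or record position, so one can say only that the supplied documents do not. The background remark that "some surgeons were reluctant to introduce direct subdural posterior fossa monitors" names a plane but is not a study instruction. The LICOX probe measures tissue oxygen, which implies a tissue position for that probe but does not fix the plane of the ICP sensor.

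A reader might infer that the plan has a false-positive rate of up to 63% or 92%. The documents do not support that. Those figures need an offset mainly in one direction, whose sign and size are not given, and a paired test that the plan does not name. A reader might also infer that only same-plane pairs should be tested. That could leave few or no pairs, and it would not deal with nearness to the lesion.

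**Conclusion.** The point holds in a limited form. On the supplied documents, sensor plane and distance from the lesion are neither stated to be recorded nor used, while a compartment-level difference is both an outcome and a hypothesis. A systematic local offset could therefore be reported as a transtentorial difference.

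The size cannot be derived from the plan. Error inflation requires an offset mainly in one direction. Under the assumed 2–5 mmHg in half the patients, it ranges from modest to severe with a paired test and is much smaller with an unpaired one. Offsets of random sign leave the error rate near 5% and cost only precision. The conclusion about labelling does not depend on any of these rates: without sensor position, the data cannot separate a gradient across the tentorium from an effect local to the operative site.

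**What to change.** No change to probe placement is proposed.

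1. Record each ICP sensor's tissue plane from the operation note, and its distance from the lesion on the CT/MRI already planned within 72 hours.
2. Name a paired within-patient comparison, keep all pairs in it, and label the contrast 'operative-site minus supratentorial' pressure. Where the usual sensor was placed at the lesion, say so.
3. Show the paired differences by plane match and by distance from the lesion, with same-plane pairs as a sensitivity analysis.
4. Claim a transtentorial gradient only if the difference persists in same-plane pairs and is not explained by nearness to the lesion.
5. If the TIBI protocol already fixes or records position for infratentorial probes, state this in the protocol.

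The cost is two data fields read from routine records and a few sentences of analysis text. The downside is small subgroups, possibly no same-plane pairs at all, and so a more cautious conclusion from a 15-patient pilot. If there are no same-plane pairs, the report should give the operative-site contrast and leave the transtentorial question open.
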